## 5 TREATMENT OF SUBJECTS AND FOLLOW-UP

### 5.1 Study Procedures

## 5.2 Study Treatment

### 5.2.1 Details of Study Treatment

WINLEVI cream 1% is supplied in [REDACTED]  
[REDACTED] 60-gram tube

### 5.2.2 Storage and Handling

WINLEVI (clascoterone) cream contains clascoterone, an androgen receptor inhibitor, in a cream base for topical dermatologic use. WINLEVI cream is a white to almost white cream. Chemically, clascoterone is [REDACTED]. Clascoterone is a white to almost white powder, practically insoluble in water. The compound has the empirical formula [REDACTED] and molecular weight of [REDACTED]. The structural formula is shown below. Each gram of WINLEVI cream 1% contains 10 mg of clascoterone in a cream base of [REDACTED].

### 5.2.3 Dispensation and Dosage Schedule

Winlevi Cream• Apply a thin layer (approximately 1 gram) to affected area twice daily (morning and evening). Avoid contact with eyes, mouth, and mucous membranes. (2) • Not for ophthalmic, oral or vaginal use. (2)

## 5.2.4 Treatment Assignment

The study medication will be administered only to eligible subjects as defined by the Study Protocol. All subjects who have signed an ICF will receive a 2-digit subject number, starting at 01. This subject number will be used to identify the subject throughout the study. Subjects withdrawn from the study will retain their subject number. New subjects will be allotted a new subject number.

### 5.2.5 Blinding, Packaging, and Labeling

Commercially available and labeled medications will be used. Medications will be dispensed in an open-label fashion.

## 5.2.6 Supplies and Accountability

The Investigator or pharmacist will inventory and acknowledge receipt of all shipments of study medication. All study medication must be kept in a locked area with access restricted to designated study personnel. The study medication must be stored in accordance with the instructions provided with the shipment. The Investigator or pharmacist will also keep accurate records of the quantities of study medication dispensed and returned by each subject.

### 5.2.7 Treatment Compliance

Subject compliance to study treatment regimen will be assessed at each visit; study personnel will ask each subject whether they missed any applications of study medication since the previous visit.

### **5.3 Concomitant Medication/Treatment**

Please see Supplement I for a listing of prohibited medications. Necessary therapies that will not interfere with the response to treatment may be provided at the discretion of the Investigator. The use of any concurrent medication, prescription or over-the-counter drug, is to be recorded in the CRF along with the reason the medication was taken.

### **5.4 Summary of known and potential risks**

### **5.5 Summary of Benefits**

There may be certain direct benefits derived from participating in this study. Such benefits include temporary, partial or complete, clearance of your acne lesions; however, it is possible that you receive no benefit. The results of this study may be useful in the development of a new therapy for others with similar conditions to yours.

## 6 STUDY ASSESSMENTS

### 6.1 Primary Endpoint

The primary endpoint of this study is the percent of patients who achieve clear or almost clear on IGA at week 16.

#### 6.1.1 Acne IGA

The Investigator will evaluate global acne severity using the following Investigator Global Assessment scale:

Score	Description
0 = Clear Skin	Clear Skin; no inflammatory or non-inflammatory lesions
1 = Almost Clear	Almost clear; rare non-inflammatory lesions with no more than one small inflammatory lesion
2 = Mild Severity	Mild severity; greater than Grade 1; some non-inflammatory lesions with no more than a few inflammatory lesions (papules/pustules only, no nodular lesions)
3 = Moderate Severity	Moderate severity; greater than Grade 2; some to many non-inflammatory lesions and may have some inflammatory lesions, but no more than one small nodular lesion
4 = Severe	Severe; greater than Grade 3; some to many non-inflammatory and inflammatory lesions, but no more than a few nodular lesions
5 = Very Severe	Very Severe; greater than Grade 4; many non-inflammatory and/or inflammatory lesions with some or many nodular lesions

### 6.2 Secondary Endpoints

1. Percent of total lesion reduction at week 16 compared to baseline
2. Percent of inflammatory lesion reduction at week 16 compared to baseline
3. Percent of non-inflammatory lesion reduction at week 16 compared to baseline.
4. Tolerability measures such as, erythema, scaling, dryness, oiliness, burning/stinging and pruritus.

#### 6.2.1 Tolerability

The Investigator will grade the current severity of erythema (disease related and/or related to IP use), dryness, peeling, and oiliness as per the following:

Score	Erythema	Dryness	Peeling	Oiliness
0 = Absent	No redness	None	Smooth	Normal
1 = Trace	Faint red or pink coloration, barely perceptible	Barely perceptible dryness by palpation with no accentuation of skin markings, skin desquamation (flakes) or fissure formation	Fine peeling, barely perceptible	Mild and localized
2 = Mild	Light red or pink coloration	Easily perceptible dryness by palpation with accentuation of skin markings but no skin desquamation (flakes) or fissure formation	Slight peeling	Mild and diffuse
3 = Moderate	Medium red coloration	Easily noted dryness with accentuation of skin markings and skin desquamation (small flakes) but no fissure formation	Definitely noticeable peeling	Moderate and diffuse
4 = Severe	Beet red coloration	Easily noted dryness with accentuation of skin markings, skin desquamation (large	Extensive peeling	Prominent and dense

The **Investigator** will **interview the subject** to determine the *current* severity of pruritus and burning/stinging; these symptoms will be graded as per the following:

Score	Description
0 = Absent	Normal, no discomfort
1 = Trace	An awareness, but no discomfort and no intervention required
2 = Mild	Noticeable discomfort causing intermittent awareness
3 = Moderate	Noticeable discomfort causing continuous awareness
4 = Marked	Definite discomfort causing continuous awareness interfering occasionally with normal daily activities
5 = Severe	Definite, continuous discomfort interfering with normal daily activities

---

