## 2 STUDY OBJECTIVES

The objectives of this study are to observe the efficacy and safety of Winlevi in skin of color patients with acne.

Primary objective: Percent of subjects who are clear or almost clear on IGA scale at week 16.

Secondary objectives:

1. Percent of subjects who are clear or almost clear at weeks [REDACTED]
2. Percent of total lesion reduction at week [REDACTED] compared to baseline
3. Percent of inflammatory lesion reduction at week [REDACTED] compared to baseline
4. Percent of non-inflammatory lesion reduction at week [REDACTED] compared to baseline.
5. Tolerability measures such as, erythema, scaling, dryness, oiliness, burning/stinging, and pruritus.

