## 4 SELECTION AND WITHDRAWAL OF SUBJECTS

### 4.1 Inclusion Criteria

- i. Outpatient, male or female subjects of any race (Fitzpatrick skin types IV, V, VI), and at least 12 years of age or older. Female subjects of childbearing potential must have a negative urine pregnancy test result at Baseline (test must have a sensitivity of at least 25mIU/ml for human chorionic gonadotropin) and practice a reliable method of contraception throughout the study:

*A female is considered of childbearing potential unless she is:*

- postmenopausal for at least 12 months prior to study drug administration;
- without a uterus and/or both ovaries; or
- has been surgically sterile for at least 6 months prior to study drug administration.

*Reliable methods of contraception are:*

- hormonal methods or intrauterine device in use  $\geq$  90 days prior to study drug administration;
- barrier methods plus spermicide in use at least 14 days prior to study drug administration; or
- vasectomized partner (vasectomy must be performed 3 months prior to first study drug administration or in the alternative a zero sperm count will suffice)

*[Exception: Female subjects of childbearing potential who are not sexually active will not be required to practice a reliable method of contraception. These subjects may be enrolled at the Investigator's discretion if they are counseled to remain sexually inactive during the study and understand the possible risks in getting pregnant during the study.]*

- ii. Facial acne IGA score of 3 or 4.
- iii. Able to understand the requirements of the study and sign Informed Consent/HIPAA Authorization forms. Subjects under the legal age of consent in the state where the study is conducted must also have the written, informed consent of a parent or legal guardian.

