### **8.2 Analyses**

Statistical analyses will be conducted on an intent-to-treat basis (i.e., all enrolled subjects will be included in the analyses). All statistical tests will be two-sided and interpreted at a 5% significance level. Descriptive statistics (i.e., mean, standard deviation, etc.) will be provided for all continuous variables and frequencies for all categorical variables collected in this study. These will be presented by treatment group. Summary tables will be used to present patient population characteristics at Baseline; data from the study questionnaires will be included. The incidence and severity of adverse and/or unexpected events will be tabulated and a complete listing of all reports of adverse and/or unexpected events will be presented.

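### Per-visit erythema frequencies cannot isolate new or worsened erythema on treatment: the score pools acne and product redness, and no comparison with the subject's own baseline is planned (low priority)

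*Combined protocol and SAP*

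**What the plan says.** - **Score.** Section 6.2.1 asks for one current-severity grade for each of "erythema (disease related and/or related to IP use), dryness, peeling, and oiliness". The published text shows no separate field for the cause of the redness.
- **Anchors.** Grade 0 is absence of redness. Grades 1 to 4 are "Faint red or pink coloration, barely perceptible", "Light red or pink coloration", "Medium red coloration" and "Beet red coloration". No erythema anchor uses a sign other than red or pink colour. Dryness, in the same table, is graded by palpation, skin markings and flaking.
- **Population.** Section 4.1 admits "subjects of any race (Fitzpatrick skin types IV, V, VI"). The aim in Section 2 is to "observe the efficacy and safety of Winlevi in skin of color patients with acne", and tolerability, with erythema named first, is a secondary item in Sections 2 and 6.2.
- **Design.** Section 3 describes a single-center, open-label pilot in which every subject receives the product. Section 8.1 sets 10 subjects.
- **Analysis.** Section 8.2 promises descriptive statistics and "frequencies for all categorical variables collected in this study". Section 6.2 words the three lesion endpoints as changes from baseline but not the tolerability item. No shift, worst-grade or treatment-emergent rule is given for the tolerability grades.
- **Other safety data.** Section 7.1 defines an adverse event as a condition absent before the study or worse during it, whatever the cause. Section 7.2.2 requires every adverse event to be recorded, and Section 8.2 tabulates and lists them. Pruritus and burning/stinging are graded by interview (6.2.1).

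**The concern.** A reader of the tolerability table will want to know how many subjects developed erythema, or had it worsen, after starting the product. A frequency at each visit does not answer that. It gives the total at each time and says nothing about which subjects moved. Subjects enter with moderate or severe facial acne, so some redness at baseline is likely. Redness that fades as acne improves and redness that appears on treatment are netted against each other in the same count, and with no control arm nothing else in the table separates them.

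A second, weaker worry concerns the anchors. A scale written only in reds and pinks is used in a study limited to the darker skin types, and it may not register inflammation that appears as another colour change.

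At stake is the erythema statement in a study whose purpose is to describe the product in skin of color. With 10 subjects, each subject moves the rate by 10 points.

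**Working it through.** The documents give no erythema rate, detection rate or precision target, so there is no planned figure to reproduce. Only n = 10 comes from the plan (8.1). The other inputs below are assumptions chosen for illustration.

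**1. What two visit frequencies can tell us.** Let *a* be the number with erythema at baseline, *b* the number on treatment, *r* the number who resolve and *x* the number of new cases. Then b = a − r + x, so x = b − a + r. The table reports *a* and *b* but not *r*.

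Take a = 6, r = 4, x = 3. Then b = 6 − 4 + 3 = 5, and the table reads 6/10 then 5/10.

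| | On treatment: yes | On treatment: no | Total |
|---|---|---|---|
| Baseline: yes | 2 | 4 | 6 |
| Baseline: no | 3 | 1 | 4 |
| Total | 5 | 5 | 10 |

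The new cases are 3/10. The Clopper-Pearson 95% limits are the 2.5% point of Beta(3, 8) and the 97.5% point of Beta(4, 7), which give 6.7% to 65.2%. This takes the two subjects with persistent erythema as not having worsened.

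The same margins fit other histories. With a = 6 and b = 5, x = r − 1, and x cannot exceed the 4 subjects who were clear at baseline. So *x* can be anything from 0 (one resolves) to 4 (five resolve): the published table would be identical for 0/10 and 4/10 new cases.

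**2. Direction of the error.** Let *p* be the true rate of product erythema, *d0* and *d1* the shares with acne redness at baseline and on treatment, and *s* the chance that redness is recorded. Assume product and acne redness are independent.

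- Recorded on treatment = s × [1 − (1 − p)(1 − d1)]
- Recorded at baseline = s × d0

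| p | d0 | d1 | s | On treatment | Change from baseline |
|---|---|---|---|---|---|
| 20% | 50% | 20% | 1 | 1 − 0.8 × 0.8 = 36% | −14 points |
| 20% | 50% | 50% | 1 | 1 − 0.8 × 0.5 = 60% | +10 points |
| 20% | 50% | 20% | 0.5 | 0.5 × 0.36 = 18% | −7 points |
| 30% | 30% | 10% | 1 | 1 − 0.7 × 0.9 = 37% | +7 points |

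With full detection, the on-treatment frequency is above the true rate in every row. The change from baseline is below it in every row, and negative where acne redness falls from 50% to 20%. In the third row, incomplete detection brings the on-treatment figure slightly under the true 20%. The sign of the error depends on which comparison is made and on inputs the documents do not give.

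**3. The anchors alone.** Setting acne redness aside, the chance of recording at least one case in 10 is 1 − (1 − p·s)^10.

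| True rate p | s = 1 | s = 0.75 | s = 0.5 |
|---|---|---|---|
| 10% | 65% | 54% | 40% |
| 20% | 89% | 80% | 65% |
| 30% | 97% | 92% | 80% |

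This shows what a given loss of detection would do. It is not evidence that the loss occurs.

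**4. Limit set by sample size.** Even with a perfect scale, 0/10 leaves an exact two-sided 95% upper limit of 1 − 0.025^(1/10) = 30.8%.

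**The case against.** **Under-counting is not established.** A reader might infer that both features of the scale favour the product, so that treatment-caused erythema will be under-counted. The documents do not support this. Pooling adds acne redness to product redness, so the on-treatment frequency in the example (5/10) exceeds the treatment-emergent count (3/10). Masking arises only when visits are compared with baseline. That comparison is a natural way to read per-visit tables, but Section 8.2 does not plan it. This objection stands.

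**Visibility of redness is not documented.** Nothing in the protocol says how well redness shows in Fitzpatrick IV-VI, or that inflamed skin of another hue would be scored 0. An investigator may grade beyond the literal wording. If the anchors do miss redness, they also miss acne redness at baseline, which shrinks the offset. This stands: the anchor point is a possibility of unknown size.

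**Other channels exist.** The adverse-event definition is itself a comparison with the pre-study state and is not tied to colour words. The symptom scores come from interview, and dryness and peeling are graded separately. It would therefore be wrong to say that the study has no means of noticing irritation. The backup is partial: no rule turns a rise in grade into an adverse event, Section 7.2.2 names no causality item, and symptomless redness could escape both channels.

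**The example is strong.** It needs 3 of the 4 subjects who were clear at baseline to develop erythema. A milder case gives the same table: 2 resolve, 1 is new, and 6/10 becomes 5/10. That the margins cannot distinguish these histories does not depend on which one is chosen.

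**It is a small pilot.** Erythema is one of six items in a secondary endpoint, and the sample size limits any conclusion. This bears on priority, and it stands.

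**Conclusion.** The point holds in a limited form. Under the plan as written, the erythema table cannot isolate new or worsened erythema on treatment, because one score covers both sources of redness, there is no control arm, and the grades are summarised only by descriptive statistics and frequencies. In the illustration, a table reading 6/10 then 5/10 is compatible with anything from 0 to 4 new cases in 10. This part rests only on the documents and on counting.

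The direction of bias is undetermined. Raw prevalence overstates product erythema when detection is full, and a comparison with baseline can hide it. The further possibility that red and pink anchors miss erythema in the enrolled skin types is reasonable to raise, but it rests on an assumption that the documents neither state nor quantify. A claim that the trial will under-count erythema goes beyond them.

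Priority is low. The measure is secondary, adverse events and interview-graded symptoms give partial cover, and neither the IGA primary endpoint nor the sample size is affected.

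**What to change.** **Change to 8.2.** For erythema and the other five tolerability items (dryness, peeling or scaling, oiliness, burning/stinging, pruritus), report:

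- the number and percent of subjects whose worst post-baseline grade exceeds their own baseline grade, with an exact 95% CI;
- a shift table of baseline grade against worst post-baseline grade.

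Keep the per-visit frequencies beside these. Confirm that all six items are graded at Baseline; the published text does not show this, and the visit details are not available to check.

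**Cost.** Additional summary output for each item, with no added visits or procedures provided the baseline grades are already collected. The new count still does not assign cause: a worst grade can also reflect an acne flare, so it should be labelled treatment-emergent, not product-caused.

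**Optional.** Before grading starts, review whether the erythema anchors in 6.2.1 suit the enrolled skin types. This is a trade-off. Wording that accepts any darkening relative to adjacent skin would also score pigment change as erythema, so revised anchors must exclude it. They would also be somewhat less comparable with studies that used a red-only scale. If the anchors stay as they are, the report should present erythema beside the burning/stinging and pruritus scores and avoid reading low erythema grades alone as absence of irritation.

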### 6.2.3 Vital Signs

The Investigator will measure vital signs (SBP, DBP, HR, T°) and weight as per his standard of care.

## 7 ASSESSMENTS OF SAFETY

### 7.1 Safety Assessments

Throughout the study, subjects will be monitored for signs and symptoms of adverse events. An *adverse event* is any pathological or unintended change in the structure, function or chemistry of the body that occurs during the study, irrespective of causality, including any illness, injury, toxicity, sensitivity, or sudden death. The condition must either not be present pre-study or must worsen in either intensity or frequency during the study.

A *serious adverse event* is any untoward medical occurrence, that, at any dose:

- results in death;
- is life-threatening;
- requires in-patient hospitalization or prolongation of existing hospitalization;
- results in persistent or significant disability/incapacity;
- is a congenital anomaly/birth defect; or
- is an important medical event.

An *unexpected adverse event* is any treatment-related adverse event, which is not identified in nature, severity, or frequency in current literature on the test product.

### 7.2 Reporting Requirements

#### 7.2.1 Serious and/or Unexpected Adverse Events

Any serious or treatment-related unexpected adverse event occurring in this study must be reported to the IRB within its stipulated reporting timelines.

#### 7.2.2 Adverse Event Reporting

All adverse events must be recorded by the Investigator into the CRF. The Investigator will be required to describe the adverse event, onset and stop date, severity, the course of action taken, if any, as well as any pertinent data necessary to allow a complete evaluation of the adverse event. For serious adverse events, an additional report (SAE report) must be completed.

### **7.2.3 Follow-up and Final Reports**

Subjects who have had a serious adverse event must be followed clinically until all parameters, including laboratory values (if applicable), have either returned to normal or are otherwise explained.

If death was the outcome of the event on the initial SAE Report, a Follow-up/Final Report, including autopsy report, when performed, must be completed.

## **8 STATISTICS**

### **8.1 Sample Size Justification**

A total of 10 subjects will be entered into the study. This is a pilot study and a formal justification for the sample size is not provided. The data from this study will provide important data for determining any trends regarding the safety and efficacy of study medication.

### **8.2 Analyses**

Statistical analyses will be conducted on an intent-to-treat basis (i.e., all enrolled subjects will be included in the analyses). All statistical tests will be two-sided and interpreted at a 5% significance level. Descriptive statistics (i.e., mean, standard deviation, etc.) will be provided for all continuous variables and frequencies for all categorical variables collected in this study. These will be presented by treatment group. Summary tables will be used to present patient population characteristics at Baseline; data from the study questionnaires will be included. The incidence and severity of adverse and/or unexpected events will be tabulated and a complete listing of all reports of adverse and/or unexpected events will be presented.

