#### **4.2 Exclusion Criteria**

- i. Female subjects who are pregnant (positive urine pregnancy test), breast-feeding, or who are of childbearing potential and not practicing a reliable method of birth control.
- ii. Allergy or sensitivity to any component of the test medications (Section 5.2).
- iii. Subjects who have not complied with the proper wash-out periods for prohibited medications (Supplement I).
- iv. Medical condition that, in the opinion of the Investigator, contraindicates the subject's participation in the clinical study.
- v. Skin disease/disorder that might interfere with the diagnosis or evaluation of acne vulgaris
- vi. Evidence of recent alcohol or drug abuse.
- vii. History of poor cooperation, non-compliance with medical treatment, or unreliability.
- viii. Exposure to an investigational drug study within 30 days of the Baseline Visit.

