#### **4.3 Withdrawal of Subjects**

It is the right and duty of the Investigator to discontinue the study participation of a subject when the subject's health or well-being is threatened by continuation in the study. Such subjects should be withdrawn from the study.

The following are circumstances that would result in the subject's discontinuation from the study:

- the subject experiences a serious adverse event rendering them unable to continue study participation;
- the subject is unable to physically or mentally tolerate the use of the test medication;
- an exclusion criterion becomes apparent at any time during the study; or
- the subject voluntarily withdraws.

In the event of premature discontinuation from the study, the Investigator should determine the primary reason for discontinuation. A subject who is withdrawn from the study prior to initiation of treatment may be replaced.

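### Does the promise in section 8.2 to include all enrolled subjects fail for week-16 lesion reduction when subjects leave under section 4.3?

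*Combined protocol and SAP*

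**What the plan says.** Section 8.2 sets the analysis population: "Statistical analyses will be conducted on an intent-to-treat basis (i.e., all enrolled subjects will be included in the analyses". For the form of the results it says: "Descriptive statistics (i.e., mean, standard deviation, etc.) will be provided for all continuous variables and frequencies for all categorical variables collected in this study". It states no rule for a missing week-16 value.

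Section 6.2 lists three lesion endpoints of the same form (total, inflammatory and non-inflammatory). The first is "Percent of total lesion reduction at week 16 compared to baseline".

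Section 4.3 introduces its list of withdrawal reasons with "The following are circumstances that would result in the subject's discontinuation from the study". Two of the four reasons are "the subject is unable to physically or mentally tolerate the use of the test medication" and "an exclusion criterion becomes apparent at any time during the study". The other two are a disabling serious adverse event and voluntary withdrawal. Exclusion criterion ii in section 4.2 is "Allergy or sensitivity to any component of the test medications", so a subject who proves sensitive during the study can also fall under section 4.3. On replacement, section 4.3 says: "A subject who is withdrawn from the study prior to initiation of treatment may be replaced".

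Section 8.1 fixes the size at 10 subjects, calls the study a pilot and gives no formal justification. Section 5.1 shows no text in the public copy, and the visit weeks in section 3 are redacted.

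**The concern.** Read together, these sections seem to promise something that cannot be delivered. A subject who leaves the study at, say, week 6 has no week-16 count, so percent reduction at week 16 is undefined for that subject. A plain mean uses only the values that exist. Followed literally, section 8.2 would give a mean in the remaining subjects and label it intent-to-treat.

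The loss need not be random. Some of those missing would be subjects who could not tolerate the product or were sensitive to it. If they also responded worse, the reported mean would be too favourable for the ten who were enrolled. The IGA responder percentage, if taken over all ten, would in effect count the same subjects as failures. Endpoints under one label would then describe different groups. A missing subject cannot be made up once treatment has begun, and in a sample of ten each one carries a tenth of the result.

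**Working it through.** **Is there a contradiction?** Set the three provisions side by side.

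- Population (8.2): all enrolled subjects.
- Follow-up (4.3): some subjects leave the study, with replacement only before treatment.
- Summary (8.2): mean, SD and further statistics, since the list is left open.

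If all ten reach week 16, all three hold. If someone leaves, they hold together once any convention for the missing value is adopted. The mean is not the cause, because a median would also need a value or a rule for that subject. The gap is not special to lesion counts either. Section 8.2 promises only frequencies for categorical variables, and section 6.1 gives no explicit status for a subject without a week-16 IGA. What remains is one unwritten convention that covers the primary and secondary endpoints alike.

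**How large could the effect be?** The plan has no figure to reproduce beyond N = 10. Every rate, mean and SD below is an assumption.

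*Chance that someone is missing.* With probability p of leaving before week 16 for each subject, P(at least one of 10) = 1 − (1 − p)^10, and P(at least two) = 1 − (1 − p)^10 − 10p(1 − p)^9.

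| p | at least one | at least two |
|---|---|---|
| 5% | 40.1% | 8.6% |
| 10% | 65.1% | 26.4% |
| 20% | 89.3% | 62.4% |

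*Shift in the mean.* Let m be the observed mean percent reduction, w the number who leave and d the value given to each leaver. The mean over all ten is [m(10 − w) + dw]/10, so the gap from the observed mean is w(m − d)/10.

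For m = 50 and d = 0, the all-ten mean is 45, 40 or 35 for w = 1, 2 or 3. For w = 2, the gap in percentage points is:

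| observed mean m | d = 20 | d = 0 | d = −25 |
|---|---|---|---|
| 30 | 2 | 6 | 11 |
| 50 | 6 | 10 | 15 |
| 70 | 10 | 14 | 19 |

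*Precision, for scale.* The 95% half-width is t × SD/√n. With SD 30 and n = 10 it is 2.262 × 30/√10 = 21.5 points. With n = 8 it is 2.365 × 30/√8 = 25.1 points, and with SD 25 it is 2.365 × 25/√8 = 20.9 points.

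**Would a written rule give a better number?** Take zero reduction for each leaver, the simplest candidate. With m = 50, an SD of 25 in the eight observed and w = 2, the mean becomes 40. The sum of squares is 7 × 25² + 8 × 50² = 24,375, so the SD over ten is √[(24,375 − 10 × 40²)/9] = 30.5. The rule therefore changes the spread as well as the centre, and it understates the result for anyone who improved before leaving. The row for m = 50 shows that the choice of d alone moves the all-ten mean from 44 to 40 to 35. A fixed rule makes the choice explicit in advance but does not recover what the missing subject would have shown.

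**The case for a change.** The best case for a change is that it costs two or three sentences and needs no new data. The plan's own withdrawal rules remove people for product-related reasons, so the missingness is plausibly informative. Section 8.1 says the study looks for trends in efficacy, so the point estimates are its main output. With ten subjects, a convention picked after the data are seen could visibly alter them. An early-termination visit, if one sits in text that is not shown, would still not supply a week-16 count.

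Much of this stands. Section 8.2 has no missing-data rule, replacement is limited as described, and an observed-case mean would not describe all ten subjects.

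Three parts do not carry. First, the direction of bias is assumed: subjects who leave voluntarily need not have done worse, and nothing in the documents ties tolerability to lesion response. Second, the split between IGA and lesion results depends on reading the same sentence in 8.2 as supplying a non-response rule for one endpoint and nothing for the other, although it gives neither explicitly. Third, the remedy is either a debatable single imputation or a matter of labelling and reporting n. The first is a preference among several defensible choices, and the second is ordinary reporting practice.

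**Conclusion.** No change is called for. The plan leaves a gap that analysts can fill sensibly. Under the stated all-enrolled population, a competent report would show each lesion mean with its n out of 10, give the reason for each early departure (section 4.3 already asks for it to be determined), and keep ten as the IGA denominator. With so few subjects, a reader can then see exactly who is missing and recompute the mean under any assumption.

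The possible effect is not trivial on the point estimate: 2 to 19 points with two leavers under the assumed values, and nothing if everyone reaches week 16. In every case shown it is smaller than the half-width of the observed mean at n = 8 (20.9 to 25.1 points for an assumed SD of 25 to 30). That does not make a bias harmless, but these are secondary endpoints of an uncontrolled pilot without formal sizing, and no stated decision turns on them. The conclusion would be different in a powered or comparative trial, where the handling of missing values could decide the result.
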